5.4.2. Dosing Interruptions/Delays due to Treatment Related Toxicity

Participants experiencing Grade 3 or 4 potentially treatment related toxicity or intolerable Grade 2 toxicity despite supportive care should have their treatment with all of the components interrupted/delayed. Appropriate follow-up assessments should be done until adequate recovery occurs as assessed by the investigator.

Re-treatment following treatment interruption for treatment related toxicity or at the start of any new cycle may not occur until all of the following parameters have been met:

- ANC \geq 1,000/mm³.
- Platelets count \geq 50,000/mm³.
- Non-hematologic toxicities have returned to baseline or Grade \leq 1 severity (or, at the investigator discretion, Grade \leq 2 if not considered a safety risk for the participant).

If a treatment delay results from worsening of hematologic or biochemical parameters, the frequency of relevant blood tests should be increased as clinically indicated.

5.4.3. If these conditions are met within 2 weeks of treatment interruption or cycle delay, investigational product(s) may be resumed. Refer to section [Dosing Interruptions/Delays due to Non-Related Events](#)

If participants require treatment interruption for reasons other than treatment-related toxicity (eg, surgery) lasting $>$ 4 weeks, treatment resumption should be decided in consultation with the Sponsor.

In the event of active SARS-CoV2 infection confirmed (positive by regulatory authority-approved test) or presumed (test pending/clinical suspicion), the following criteria apply:

- For symptomatic participants with active SARS-CoV2 infection, investigational treatment should be delayed for at least 14 days from start of symptoms.
- This delay is intended to allow resolution of symptoms of SARS-CoV2 infection.
- Prior to restarting treatment, the participants should be afebrile for 72 hours and SARS-CoV2-related symptoms should have recovered to \leq Grade 1 for a minimum of 72 hours.
- Discuss with the Sponsor prior to restarting treatment.
- Consider potential drug-drug interactions (as described per study protocol) for any concomitant medication administered for treatment of SARS-CoV2 infection.

Dose Reductions for adverse events requiring dose reduction at the time of treatment resumption.

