Non-hematologic	Continue at the same dose level.	For pneumonitis, endocrinopathy, colitis, creatinine, AST, ALT, or total bilirubin elevations, withhold dose until toxicity is Grade ≤ 1 , or has returned to baseline, then resume at the same dose level or reduce by 1 level (considering each compound separately) at the discretion of the investigator. For all other events, continue at the same dose level.	For pneumonitis, colitis, endocrinopathy, creatinine, AST, ALT or total bilirubin elevations, or pruritus discontinue treatment.** For all other events withhold dose until toxicity is Grade ≤ 1 , or has returned to baseline, then resume treatment at the same dose level or reduce the dose by 1 level (considering each compound separately) at the discretion of the investigator.* Treatment may resume with VBIR-2 with an interruption of sasanlimab for one dose at the discretion of the investigator.	Discontinue treatment.**
Hematologic	Continue at the same dose level.	Continue at the same dose level.	Withhold dose until toxicity is Grade ≤ 2 , or has returned to baseline, then resume treatment at the same dose level.	Discontinue treatment.**

* Nausea, vomiting, or diarrhea must persist at Grade 3 despite maximal medical therapy to require dose modification.

** For Grade ≥ 3 colitis or pneumonitis, discontinue treatment permanently. For any grade of myocarditis discontinue treatment permanently. For all other conditions participants may be allowed to remain in the study to receive the VBIR-2 2 after the toxicity is Grade ≤ 1 or returned to baseline, and only if agreed upon by the Investigator and Sponsor.

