Appendix 5. Management of Immune-related Adverse Events (irAEs)

Management of irAEs including Myasthenia Gravis		
Gastrointestinal irAEs		
Severity of Diarrhea/Colitis (NCI-CTCAE v5.0)	Initial Management	Follow-up Management
Grade 1 Diarrhea: <4 stools/day over Baseline Colitis: asymptomatic	-Continue study treatment. -Symptomatic treatment (eg, loperamide).	-Close monitoring for worsening symptoms. -Educate patient to report worsening immediately. -If worsens: Treat as Grade 2, 3 or 4.
Grade 2 Diarrhea: 4 to 6 stools per day over Baseline; IV fluids indicated <24 hours; not interfering with ADL Colitis: abdominal pain; blood in stool	-Withhold study treatment. -Symptomatic treatment.	-If improves to Grade ≤ 1 : Resume study treatment. -If persists >5-7 days or recurs: Treat as Grade 3 or 4.
Grade 3 to 4 Diarrhea (Grade 3): ≥ 7 stools per day over Baseline; incontinence; IV fluids ≥ 24 h; interfering with ADL Colitis (Grade 3): severe abdominal pain, medical intervention indicated, peritoneal signs Grade 4: life-threatening, perforation	-Withhold for Grade 3. -Permanently discontinue study treatment for Grade 4 or recurrent Grade 3. -1.0 to 2.0 mg/kg/day prednisone IV or equivalent. -Add prophylactic antibiotics for opportunistic infections. -Consider lower endoscopy.	-If improves: -Continue steroids until Grade ≤ 1 , then taper over at least 1 month; resume study treatment following steroids taper (for initial Grade 3). -If worsens, persists >3 to 5 days, or recurs after improvement: -Add infliximab 5mg/kg (if no contraindication). -Note: infliximab should not be used in cases of perforation or sepsis.

Dermatological irAEs		
Grade of Rash (NCI-CTCAE v5.0)	Initial Management	Follow-up Management
Grade 1 to 2 Covering \leq 30% body surface area	
 -Continue study treatment. -Symptomatic therapy (for example, antihistamines, topical steroids). 	
 -If persists >1 to 2 weeks or recurs: 
 -Withhold study treatment; -Consider skin biopsy. -Consider 0.5-1.0 mg/kg/day prednisone or equivalent. Once improving, taper steroids over at least 1 month, consider prophylactic antibiotics for opportunistic infections, and resume study treatment following steroids taper. -If worsens: Treat as Grade 3 to 4.

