Grade 1 Grade 1 AST or ALT > ULN to 3.0 x ULN and/or Total bilirubin > ULN to 1.5 x ULN	-Continue study treatment.	-Continue liver function monitoring. -If worsens: Treat as Grade 2 or 3 - 4.
Grade 2 AST or ALT >3.0 to \leq 5 x ULN and/or total bilirubin >1.5 to \leq 3 x ULN	-Withhold study treatment. -Increase frequency of monitoring to every 3 days.	-If returns to Grade \leq 1: -Resume routine monitoring; resume study treatment. -If elevation persists >5 to 7 days or worsens: -Treat as Grade 3 to 4.
Grade 3 to 4 AST or ALT >5 x ULN and/or total bilirubin >3 x ULN	-Permanently discontinue study treatment. -Increase frequency of monitoring to every 1 to 2 days. -1.0 to 2.0 mg/kg/day prednisone or equivalent. -Add prophylactic antibiotics for opportunistic infections. -Consult gastroenterologist/hepatologist. -Consider obtaining MRI/CT scan of liver and liver biopsy if clinically warranted.	-If returns to Grade \leq 1: -Taper steroids over at least 1 month. -If does not improve in >3 to 5 days, worsens or rebounds: -Add mycophenolate mofetil 1 gram (g) twice daily. -If no response within an additional 3 to 5 days, consider other immunosuppressants per local guidelines.

Renal irAEs		
Grade of Creatinine Increased (NCI-CTCAE v5.0)	Initial Management	Follow-up Management
Grade 1 Creatinine increased > ULN to 1.5 x ULN	-Continue study treatment.	-Continue renal function monitoring -If worsens: Treat as Grade 2 to 3 or 4.
Grade 2 to 3 Creatinine increased >1.5 and ≤6 x ULN	-Withhold study treatment. -Increase frequency of monitoring to every 3 days. -1.0 to 2.0 mg/kg/day prednisone or equivalent. -Add prophylactic antibiotics for opportunistic infections. -Consider renal biopsy.	-If returns to Grade ≤ 1 : -Taper steroids over at least 1 month, and resume study treatment following steroids taper. -If worsens: -Treat as Grade 4.
Grade 4 Creatinine increased >6 x ULN	-Permanently discontinue study treatment. -Monitor creatinine daily. -1.0 to 2.0 mg/kg/day prednisone or equivalent. -Add prophylactic antibiotics for opportunistic infections Consider renal biopsy. -Nephrology consult.	-If returns to Grade ≤ 1 : Taper steroids over at least 1 month.

[figure not shown]
Cardiac irAEs		
Myocarditis	Initial Management	Follow-up Management

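### A persistent, then recovering, immune-related Grade 2 liver-test elevation leads to a permanent stop under Appendix 5 but to resumption under Table 12, and no text says which governs

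*Protocol*

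**What the plan says.** **Appendix 5, hepatic events.** At Grade 2, treatment is withheld and may restart once the value is back to Grade 1 or lower. "If elevation persists >5 to 7 days or worsens", the instruction becomes "Treat as Grade 3 to 4". That row opens with "Permanently discontinue study treatment", and its follow-up column covers a steroid taper and further immunosuppression but no restart.

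**Table 12 (Section 5.4.5.3).** The Grade 2 non-hematologic cell lists AST, ALT and total bilirubin by name. The dose is withheld until Grade 1 or lower "or has returned to baseline, then resume at the same dose level or reduce by 1 level (considering each compound separately"), at the investigator's discretion. The cell has no time limit. For Grade 2 events it does not list, it says "For all other events, continue at the same dose level".

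**Sections 5.4.2 and 5.4.3.** "If these conditions are met within 2 weeks of treatment interruption or cycle delay, investigational product(s) may be resumed". (This sentence is printed as the heading of 5.4.3 but completes 5.4.2.) Beyond 2 weeks, permanent discontinuation is to be considered rather than required.

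**Appendix 5, rash Grade 1 to 2.** Treatment continues at first. "If persists >1 to 2 weeks or recurs", the action is "Withhold study treatment", with treatment resumed later.

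**Links between the texts.** Section 5.4.5.3 cites the Appendix 5 algorithms, liver and skin included. It introduces Table 12 as general rules from which the investigator and sponsor may depart in specific cases. Table 6 (AdC68) excludes immune-related events managed under Appendix 5 from its non-hematologic row. Table 12 has no such exclusion.

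**The concern.** Two parts of one protocol give opposite instructions for the same event in the same participant: one ends treatment for good, the other restarts it. If sites follow different pages, the number of permanent discontinuations and dose interruptions partly reflects which page was read. Safety and tolerability is a primary objective of Part 2 (Section 2.2), and SAP Section 8.3.3 plans summaries of discontinuations, temporary discontinuations and dose reductions due to adverse events.

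There is a possible second effect. The other Part 2 primary endpoint, the clinical benefit rate (CBR), counts stable disease only if it lasts more than 6 months. The tumor-assessment note in the Part 2 Schedule of Activities runs routine imaging only until permanent discontinuation or another listed end point. A participant with stable disease who is stopped before 6 months may therefore lack the scans that would show it.

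**Working it through.** The plan states no figure on this point, so the check sets the passages side by side and follows three cases through each.

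**Case A: immune-related Grade 2 ALT elevation, back to Grade 1 on day 10.** Day 10 is past both ends of the Appendix 5 range (10 > 7) and inside the general 2-week window (10 < 14).

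| Text | Instruction |
|---|---|
| Appendix 5, hepatic Grade 2 | Already moved to the Grade 3 to 4 row: permanent discontinuation |
| Table 12, Grade 2 | Withheld, then resumed at the same or one lower level |
| Sections 5.4.2/5.4.3 | Resumption permitted |

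The permanent stop is reached in two steps: the Grade 2 row sends the event to the Grade 3 to 4 row, and that row ends treatment. Handling the escalated event in Table 12's Grade 3 cell does not remove the conflict. The double-asterisk footnote there still lets participants return to VBIR-2 after recovery if investigator and sponsor agree, except after Grade 3 or higher colitis or pneumonitis, or any myocarditis. The Appendix 5 hepatic Grade 3 to 4 row offers no return.

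**Case B: Grade 2 rash lasting 3 weeks.** Appendix 5 withholds, because 3 weeks exceeds 2. Table 12 does not list rash, so its instruction for unlisted Grade 2 events applies and dosing continues. For Grade 1 rash, Table 12 also continues. The mismatch is real but smaller, since the Appendix 5 withhold ends in resumption.

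**Case C: gastrointestinal Grade 2.** Appendix 5 has a similar 5-to-7-day escalation here, while Table 12 withholds Grade 2 colitis and then resumes. The receiving row in Appendix 5 allows a restart after taper for a first Grade 3 event, so the consequence differs from the hepatic one. This row should be checked with the others.

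**Is there a tie-breaker?**
- Section 5.4.5 says no specific adjustment is recommended for Grade 1/2 toxicity unless specified elsewhere, and defers to medical judgment.
- Section 5.4.5.3 cites Appendix 5 and calls Table 12 general.
- Table 6 has an explicit exclusion; Table 12 does not.
- The sasanlimab limit of more than 4 weeks, in the text above Table 12, concerns length of interruption and leads only to considering discontinuation.

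None of these says whether Appendix 5 or Table 12 governs an immune-related liver event.

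**The case against.** The strongest defense is that a specific algorithm naturally prevails over a table described as general, and that departures are left to investigator and sponsor. The 2-week rule only permits resumption, so a stricter organ-specific rule need not contradict it. Both points have force, and many sites may read it that way. But the protocol does not say so, and the sponsor wrote the exclusion into Table 6 and not into Table 12, which covers the two checkpoint inhibitors. Table 12 also names the liver tests, so it is not silent on them.

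Several stronger readings are tempting, and the documents do not support them:

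- **Every Grade 2 elevation recovering in the second week is affected.** Appendix 5 covers immune-related events only. Table 12 covers all toxicity related to sasanlimab or tremelimumab. Elevations not judged immune-related, for example from liver metastases, fall outside Appendix 5.
- **The rash conflict is equally serious.** Its withhold is temporary, and Section 5.4.2 already interrupts for intolerable Grade 2 toxicity despite supportive care. With doses every 4 weeks in Cycles 1 and 2, a short rash may fall between doses.
- **CBR moves as much as the discontinuation rate.** A complete or partial response counts without the 6-month condition. Participants already past 6 months, or who would progress sooner, are unaffected. An end-of-treatment scan is due if the last is more than 6 weeks old, and an optional post-treatment imaging entry appears in the Part 2 schedule, although its column is unclear.
- **The day ranges are themselves an error.** With checks every 3 days (days 3, 6, 9), day 6 lies between 5 and 7, so Appendix 5 is undetermined there. Ranges recur throughout Appendix 5, consistent with room for judgment. Requiring a single day count would go beyond reconciliation.

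**Conclusion.** The point holds in limited form. For an immune-related Grade 2 AST, ALT or bilirubin elevation that outlasts the Appendix 5 range and then recovers, the protocol directs a permanent stop in one place and a resumption in another, without precedence. Rash is a lesser mismatch, and the gastrointestinal row needs the same check.

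The consequence is inconsistent permanent discontinuation and interruption across sites. For CBR it is a possible loss of imaging, confined to participants with stable disease who are stopped before 6 months and would otherwise have remained stable.

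No size can be stated, because the documents give no incidence for these events. With about 30 participants in Part 2 (Section 9.3), each one classified differently would move the discontinuation proportion by 1/30 = 3.3 percentage points. That is a unit of measure, not an estimate of how many there would be. The conclusion rests on the event being judged immune-related and on sites not sharing an unwritten convention. It takes no view on which clinical rule is right.

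**What to change.** Reconcile the Appendix 5 hepatic Grade 2, rash Grade 1 to 2 and gastrointestinal Grade 2 rows, and the rows they lead to, with the matching Table 12 cells and footnote and with the 2-week provisions in Sections 5.4.2 and 5.4.3. State which text governs immune-related events, for example through an exclusion in Table 12 like the one in Table 6, or by aligning the cells so that no precedence is needed. The clinical rule, and whether to keep any duration limit, are for the sponsor to decide.

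The cost is wording in a protocol amendment: a precedence statement, or edits to these rows and cells, plus notice to sites. Sample size, endpoints and planned analyses do not change.

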Appendix 6. Recommended Management Algorithm for Myasthenia Gravis

Appendix 7. Alternative Measures During Public Emergencies

The alternative study measures described in this section are to be followed during public emergencies, including the COVID-19 pandemic. This appendix applies for the duration of the COVID-19 pandemic and will become effective for other public emergencies only upon written notification from Pfizer.

Use of these alternative study measures are expected to cease upon the return of business as usual circumstances (including the lifting of any quarantines and travel bans/advisories).

Eligibility

While SARS-CoV2 testing is not mandated for this study, local clinical practice standards for testing should be followed. A participant should be excluded if he/she has a positive test result for SARS-CoV2 infection, is known to have asymptomatic infection, or is suspected of having SARS-CoV2. Participants with active infections are excluded from study participation as per exclusion criterion #9 (Part 2): Active and clinically significant bacterial, fungal or viral infection. When the infection resolves, the participant may be considered for re-screening.

Alternative Facilities for Safety Assessments

Laboratory Testing

If a study participant is unable to visit the site for protocol-specified safety laboratory evaluations, testing may be conducted at a local laboratory if permitted by local regulations. The local laboratory may be a standalone institution or within a hospital. The safety laboratory evaluations included in Section 7.1.3 may be performed at a local laboratory.

If a local laboratory is used, qualified study site personnel must order, receive, and review results prior to dosing. Site staff must collect the local laboratory reference ranges and certifications/accreditations for filing at the site. Laboratory test results are to be provided to the site staff as soon as possible. The local laboratory reports should be filed in the participant's source documents/medical records. Relevant data from the local laboratory report should be recorded on the CRF.

Study Intervention

If the safety of a trial participant is at risk because they cannot complete required evaluations or adhere to critical mitigation steps, then discontinuing that participant from study intervention must be considered.

The following is recommended for the continued administration of the investigational products for participants who have active confirmed (positive by regulatory authority-approved test) or presumed (test pending/clinical suspicion) SARS-CoV2 infection:

- For symptomatic participants with active SARS-CoV2 infection, study intervention should be delayed for at least 14 days from the start of symptoms. This delay is intended to allow the resolution of symptoms of SARS-CoV2 infection.
- Prior to restarting treatment, the participant should be afebrile for 72 hours, and SARS-CoV2-related symptoms should have recovered to \leq Grade 1 for a minimum of 72 hours. Notify the study team when treatment is restarted.
- Continue to consider potential drug-drug interactions as described in Section [5.7](#) for any concomitant medication administered for treatment of SARS-CoV2 infection.

Adverse Events and Serious Adverse Events

If a participant has COVID-19 during the study, this should be reported as an AE or SAE and appropriate medical intervention provided. Temporary discontinuation of the study intervention may be medically appropriate until the participant has recovered from COVID-19.

It is recommended that the investigator discuss temporary or permanent discontinuation of study intervention with the study medical monitor.

1. AMENDMENTS FROM PREVIOUS VERSION(S)

None.

2. INTRODUCTION

PF-06936308 is a vaccine-based immunotherapy regimen-2 (VBIR-2) that is currently being investigated in patients with advanced non-small cell lung cancer (NSCLC) and metastatic triple-negative breast cancer (mTNBC). The protocol C3621001 outlines the VBIR-2 study for Part 1 (dose escalation).

This document describes the planned statistical analyses for Protocol C3621001, dated 16 March 2018. This SAP is meant to supplement the study protocol. This SAP supersedes the statistical considerations identified in the protocol and, where considerations are substantially different they will be identified as such. Any deviations from this analysis plan will be described in the clinical study report (CSR). Any post-hoc, or unplanned analyses performed that are not specified in this SAP will be clearly identified in the CSR. This plan is developed and finalized prior to database lock of the clinical database. This SAP is written with consideration of the recommendations outlined in the International Conference on Harmonisation (ICH) E9 Guideline (Guidance for Industry: Statistical Principles for Clinical Trials) and on the ICH E3 Guideline (Guidance for Industry: Structure and Content of Clinical Study Reports).

Note: in this document any text taken directly from the protocol is *italicized*.

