9. DATA ANALYSIS/STATISTICAL METHODS

Detailed methodology for summary and statistical analyses of the data collected in this study is outlined here and further detailed in a statistical analysis plan (SAP), which will be maintained by the sponsor. The SAP may modify what is outlined in the protocol where appropriate; however, any major modifications of the primary endpoint definitions or their analyses will also be reflected in a protocol amendment.

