9.3. Sample Size Determination

It is anticipated that each of the cohorts will aim to enroll 2-4 participants, with the exception of the cohort with the anticipated MTD dose that will aim to enroll up to 12 participants. Due to the dynamic nature of the Bayesian allocation procedure, the sample size of the mTPI approach cannot be determined in advance. It is estimated approximately 36 DLT evaluable participants may be enrolled in the dose escalation stage in order to have a reliable and accurate estimate of the MTD. The actual sample size for the dose escalation may be smaller, depending on the underlying dose toxicity profile.

At least 6 and up to 12 participants should be enrolled at a dose level that is predicted to be the MTD as per the mTPI method. Dose cohorts with an acceptable safety profile may be expanded up to N=12 to further assess safety, CCI [REDACTED] pharmacokinetics, CCI [REDACTED] [REDACTED] Decisions to enroll additional participants at dose levels already cleared for safety will be based on clinical judgment of the investigators and the sponsor considering all evaluable safety, CCI [REDACTED] data.

The expansion phase of the study (Part 2) will consist of 1 cohort of participants with metastatic or locally-advanced NSCLC. Approximately 30 participants will be enrolled for

the dose expansion. A Bayesian approach will be used to estimate the objective response rate (ORR) and clinical benefit rate (CBR) in the study indications. As an example of this approach related to ORR, assuming a non informative prior (ie, Jeffrey's prior), if 14 out of 30 participants (46.7%) achieve a CR or PR, this would translate into a posterior probability (Beta Binomial) of 77% that the true ORR/clinical benefit rate is not inferior to 20%. (See Definitions of ORR and CBR in Section 9.4).

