2.1. Study Design

This is a Phase 1, open label, multi-center, multiple dose, safety, PK, PD and immunogenicity study evaluating the components of VBIR-2 (PF-06936308) in patients with advanced NSCLC and metastatic TNBC. VBIR-2 consists of the following components: AdC68, pDNA, tremelimumab and anti-PD-1 (PF-06801591).

The study is divided into two parts, dose escalation (Part 1) followed by dose expansion (Part 2). The Part 2 dose expansion protocol specifics will be covered in a subsequent amendment once recommended phase 2 dose (RP2D)/MTD is reached in Part 1. The dose escalation (Part 1) is anticipated to have 7 cohorts and estimated to enroll approximately 36 patients in Part 1. The actual number of patients enrolled will depend on the tolerability of the components of the VBIR-2.

[figure not shown]
Part 1 (dose escalation) will include patients with advanced NSCLC and mTNBC for whom no standard therapy is available. Length of treatment is estimated to be 8-22 months, depending on each patient's disease status.

The proposed doses, schedule(s), and PK time points may be reconsidered and amended during the study based on the emerging safety and PK data. The dose level to be carried forward in subsequent cohorts may be different than those depicted in Table 2. If the highest tested dose of one component is not tolerable, then a lower or intermediate dose could be

carried forward in subsequent cohorts. If a component is not tolerable, it could be excluded from the dose escalation.

The overall design is presented in Figure 1.

Figure 1. Overall Study Design Part 1

Maintenance Treatment Schedule for anti-PD-1 (PF-06801591) starting at Month 9, will continue to be administered every 4 weeks.

Maintenance Treatment Schedule for pDNA and tremelimumab after Month 8 will be administered every 8 weeks starting with Month 10.

Treatment will be continued until disease progression, unacceptable toxicity, death, or patient's or investigator's decision.

Part 2 (dose expansion) will require a protocol amendment; only a high level study design is described below. Details of the patient population, inclusion-exclusion criteria, and detailed

study design with statistical calculations will be covered in a subsequent amendment once RP2D/MTD is reached in Part 1.

Part 2 will enroll patients in a design with 3 simultaneous non-randomized cohorts to further evaluate the safety and antitumor activity of the VBIR-2 regimen in patients with advanced NSCLC and mTNBC.

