4. HYPOTHESES AND DECISION RULES

4.1. Statistical Hypotheses

The expansion phase of the study (Part 2) will consist of three single arm cohorts: Cohort 1B, 2B and 3B respectively; the recommended dose from Part 1 will be used in this phase. Approximately n=15 patients would be enrolled in Cohort 1B of mNSCLC \geq 2L PD-L1 negative patients and n=20 in Cohort 2B, approximately n=10 mNSCLC \geq 2L patients who are PD-L1 positive >1% and <50% and n=10 mNSCLC \geq 2L patients who are PD-L1 positive \geq 50%. For the mTNBC cohort, the study will enroll n=26 patients and have approximately 80% power with 1-sided alpha=0.1 to detect an ORR of 50% with a null hypothesis of 30% ORR.

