8. STATISTICAL METHODOLOGY AND STATISTICAL ANALYSES

8.1. Statistical Methods

CCI

Part

2 (dose expansion) will require a protocol amendment; only a high level study design is described in the protocol. For the mTNBC cohort, the study will enroll n=26 patients and have approximately 80% power with 1-sided alpha=0.1 to detect an ORR of 50% with a null hypothesis of 30% ORR.

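### The supplied SAP was not updated for Amendment 2, so its readable text has no analysis of the Part 2 primary endpoint CBR, and the Bayesian example in protocol 9.3 is numerically wrong

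*SAP*

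**What the plan says.** **Version.** SAP 2 states: "This document describes the planned statistical analyses for Protocol C3621001, dated 16 March 2018". SAP 1 lists no amendments, and SAP 2 says the SAP takes precedence over the protocol's statistical text. The current protocol is Amendment 2 (22 December 2020). Protocol 9 says that the methodology is "outlined here and further detailed in a statistical analysis plan (SAP), which will be maintained by the sponsor".

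**Part 2 in the SAP.** SAP 2.1 says "Part 2 (dose expansion) will require a protocol amendment; only a high level study design is described below" and that a detailed "study design with statistical calculations will be covered in a subsequent amendment". SAP 4.1 nevertheless states: "The expansion phase of the study (Part 2) will consist of three single arm cohorts: Cohort 1B, 2B and 3B respectively". SAP 8.1 repeats a test: "For the mTNBC cohort, the study will enroll n=26 patients and have approximately 80% power with 1-sided alpha=0.1", for an ORR of 50% against 30%. SAP 3 announces a Part 2 futility check and sends the reader to Section 4 for it.

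**Part 2 in the protocol.** Section 9.3 says "The expansion phase of the study (Part 2) will consist of 1 cohort of participants with metastatic or locally-advanced NSCLC" and gives the size as "Approximately 30 participants will be enrolled for" the expansion. Section 2.2 makes CBR (CR, PR, or SD for more than 6 months) a primary endpoint alongside safety, with ORR, DOR, PFS and OS secondary. Section 9.3 plans Bayesian estimation of ORR and CBR. Its example takes 14 responders out of 30 under a Jeffreys prior and reports 77% posterior probability that the rate is not inferior to 20%.

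**Endpoints in the SAP.** SAP 6.2.1 names DLT as the study's primary endpoint; protocol 9.5.1 limits that to Part 1. SAP 6.1 defines PFS, OS, DOR and DOSD and derives best response and ORR, but its readable text does not mention CBR. It uses unconfirmed best response over all assessments, and the reason it gives is that response rate is not primary.

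**The concern.** The protocol looks to the SAP for analysis detail. The supplied SAP looks to a later protocol amendment for the Part 2 calculations. Amendment 2 then supplied a cohort, a size, a CBR definition, a prior and an estimator, but the SAP was not brought into line.

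The derivation rules for a primary endpoint in an open-label single-arm cohort are therefore not prespecified in what was supplied. They would be fixed late, or inherited by default from SAP 6.1. If that best-response rule were carried over, a PR seen on one scan, or a PR after a first RECIST progression, would count as clinical benefit. Scans after progression are foreseeable, because protocol 3.1.2 encourages participants to stay on treatment for at least 24 weeks. The SAP's stated reason for leaving CR and PR unconfirmed also lapses in Part 2, where both count toward primary CBR.

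The one worked example a programmer could use to check the Bayesian method gives the wrong answer.

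**Working it through.** **1. Part 2 size and power in the SAP.** Inputs are from SAP 2.1 and 4.1. Total: 15 + 20 + 26 = 61 in three cohorts, against about 30 in one cohort in protocol 9.3.

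The SAP's power figure reproduces by normal approximation with n = 26, p0 = 0.30, p1 = 0.50 and one-sided alpha 0.10:

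- power = Φ{[√26 × 0.20 − 1.2816 × √(0.30 × 0.70)] / √(0.50 × 0.50)}
- = Φ[(1.0198 − 0.5873) / 0.5] = Φ(0.865) = 0.806

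So about 80% is right for that method, but it describes an mTNBC cohort that protocol 1.2.1 excludes from Part 2.

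**2. The example in protocol 9.3.** Inputs: x = 14, n = 30, Jeffreys prior Beta(0.5, 0.5). The posterior is Beta(x + 0.5, n − x + 0.5) = Beta(14.5, 16.5).

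| Quantity | Result |
|---|---|
| P(rate > 20%), Jeffreys | 0.9995 |
| P(rate > 40%), Jeffreys | 0.773 |
| Threshold at which the probability is 0.77 | 0.401 |
| P(rate > 20%), uniform prior, Beta(15, 17) | 0.9996 |
| 95% credible interval, Jeffreys | 29.8% to 64.1% |

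The stated 77% at 20% does not reproduce. Changing only the count does not rescue it: at a 20% threshold, 7/30 gives 0.689 and 8/30 gives 0.822, and the probability rises with x, so no whole count out of 30 gives 0.77. A uniform prior does not rescue it either.

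**3. The futility reference.** SAP 3 points to Section 4. SAP 4.1 holds cohort sizes and one power statement. SAP 4.2 points only to the dose-escalation rule. No futility boundary is stated, and no redaction mark appears in Section 4.

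**4. Day count for SD longer than 6 months.** The Part 2 schedule has scans every 8 weeks, ±5 days, to Week 32. The footnote to the Part 2 maintenance schedule defines a month as 28 days.

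- 28-day months: 6 × 28 = 168 days, the nominal day of the Week 24 scan, whose window is days 163 to 173. Scans on days 163 to 168 do not exceed 168; those on days 169 to 173 do.
- Calendar months: 6 × 365.25 / 12 = 182.6, about 183 days. No day in the Week 24 window reaches this, so the Week 32 scan (224 ± 5, days 219 to 229) is needed.

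The unstated convention therefore decides which scan qualifies a participant.

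**5. Weight of one participant.** 1/30 = 3.3 percentage points of CBR for each person counted only through a one-scan PR or a PR after progression. The documents give no basis for how many there would be.

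**6. Protocol 9.4 against 2.2.** Section 9.4 describes anti-tumor activity as secondary, in a sentence cut by a redaction. Section 2.2 lists it twice for Part 2: as primary through CBR, and as secondary through ORR, DOR, PFS and OS. The description in 9.4 is incomplete.

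**The case against.** The strongest reply is that this is largely a version gap. The SAP declares which protocol it covers, labels its Part 2 text as high level, and says that details will follow. It is to be finalized before database lock and is maintained by the sponsor, so an updated version may exist. All of that stands. It means that 61 against about 30 compares a flagged placeholder with the governing protocol. A reader might infer that enrolment could follow the wrong number; the documents do not support that.

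Three other stronger readings also fail:

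- *That the SAP has no Bayesian method.* It uses a beta-binomial model for DLTs in Part 1; what is missing is an estimator for ORR and CBR. SAP 6.1 and 8.1 open with redactions, so the statement applies to the readable text only.
- *That protocol 9.4 flatly contradicts 2.2.* A secondary anti-tumor objective does exist; 9.4 omits the primary one.
- *That the wrong example could change a trial decision.* The protocol attaches no rule to the posterior, so no such effect is shown.

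The reply does not reach the arithmetic in 9.3, which is in the current protocol and was added with Amendment 2's Part 2 sample size. Nor does it reach the futility reference, which is empty within the SAP itself.

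**Conclusion.** The point holds. The supplied SAP disagrees with the current protocol on Part 2 cohorts, size and primary endpoint. Its readable text contains no CBR definition and no estimator for ORR or CBR, and its reason for using unconfirmed response no longer applies to Part 2. In protocol 9.3, 14/30 gives 0.9995 at 20%, not 77%.

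The effect on the reported CBR is not known. It is 3.3 points per participant counted only through a one-scan or post-progression response, and it arises only if the SAP 6.1 rule is carried over. The conclusion assumes that no later SAP exists, or that a later one has the same gaps, and that the redacted openings of SAP 6.1 and 8.1 do not contain the CBR analysis. That second assumption is reasonable, because the amendment log shows CBR being added to protocol 9.4 only in Amendment 2. The 9.3 result depends on neither assumption.

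**What to change.** 1. **Protocol 9.3.** Make the count, threshold and probability agree. For 14/30, state 99.95% at 20%, or 77% at 40%.
2. **SAP 2.1, 3, 4.1 and 8.1.** Replace the Part 2 text with the single NSCLC cohort of about 30 and remove the mTNBC test. Either state the futility rule or delete the reference to it; that is the sponsor's choice.
3. **SAP 6.** Limit DLT as primary endpoint to Part 1. Add CBR as the Part 2 primary efficacy endpoint with the Jeffreys beta-binomial posterior, a 95% credible interval, one named analysis set (mITT or EP, both named in protocol 9.4), and an explicit day count for SD longer than 6 months.
4. **Response confirmation.** Restate the reason for using unconfirmed response now that CBR is primary. Add a sensitivity analysis with CR or PR confirmed at least 4 weeks later on scheduled scans, and best response taken only up to first RECIST progression.
5. **Protocol 9.4.** For Part 2, describe CBR as primary and the other anti-tumor endpoints as secondary.
6. **Minor clean-up.** Align the CTCAE version in SAP 6.2.1 (4.03) with the protocol's 5.0, plan Kaplan-Meier as protocol 9.4 does, and delete the irRECIST summaries or label them exploratory.

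The cost is a SAP amendment, some programming, and protocol corrections to 9.3 and 9.4. No scans are added, because the sensitivity analysis uses the 8-weekly scans to Week 32 and the 12-weekly scans after that. Its drawback is that responders who stop before their next scan stay unconfirmed.
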